1.5 Study Agents

There are no drugs included within the arms of the trial as experimental agents, although the use of endocrine agents (tamoxifen or aromatase inhibitors) as adjuvant therapy within both arms of the trial are encouraged to be considered and adherence be recorded. Such endocrine agents have many decades of use in standard clinical practice and have extensive safety profiles. In the setting of DCIS, tamoxifen in both pre- and post-menopausal women is associated with reduction in the risk of ipsilateral and contralateral breast cancer events. Recent studies comparing the aromatase inhibitor anastrozole to tamoxifen in post-menopausal women have revealed that the aromatase inhibitor is similarly to slightly more effective with regard to efficacy.

Side effects and adverse events do vary between the two agents and this factor may be the rationale for choosing one agent over the other in post-menopausal women (for premenopausal women, tamoxifen is the primary hormonal therapy option).^{38,59} Risks of tamoxifen include but are not limited to hot flashes, night sweats, vaginal discharge, premature cataracts as well as more serious but rare risks of uterine cancer and thrombosis. Risks of anastrozole include but are not limited to hot flashes, night sweats, vaginal dryness, musculoskeletal symptoms as well as increased risk of osteoporosis and fractures. Recent patients reported outcomes data from the NSABP B-35 trial comparing adjuvant tamoxifen to anastrozole in post-menopausal women with DCIS suggested that women treated with tamoxifen had increased severity of vasomotor symptoms, bladder control and gynecologic symptoms compared to women treated with anastrozole who reported increased severity of musculoskeletal and vaginal symptoms.^{38,59} Of note, benefits were greatest in women under 60, particularly for women receiving anastrozole, but in

both arms these younger women reported had significantly worse vasomotor, vaginal and gynecologic symptoms as well as more weight gain.

1.6 Risks and Benefits

Surgery is, by definition, the prevailing standard of care for DCIS. The risks associated with surgical management of a breast lesion are well documented and include, but are not limited to, surgical and anesthetic side effects and/or complications; side effects and complications of subsequent radiotherapy following breast conservation therapy, if utilized; side effects and complications of endocrine therapy, if prescribed and taken. All local treatments may also be associated with a negative impact on cosmesis.

For surgery, the potential benefits (while uncertain on an individual patient basis) include reduced incidence of invasive breast cancer and reduced recurrence of DCIS or invasive breast disease. For endocrine therapy the impact on ipsilateral DCIS or recurrence/invasive breast cancer is uncertain, although there is a clear population-based reduction in contralateral DCIS and invasive breast cancer.

For AM, the risk of progression of DCIS to more extensive involvement of the breast or to developing invasive breast cancer is a key clinical outcome of the trial. The greatest potential risk to patients is posed by the delay in diagnosis of invasive breast cancer as a result of understaging on core biopsy. Among women who are diagnosed with low or intermediate grade DCIS without invasive breast cancer on core biopsy, the estimate of upstaging to invasive cancer upon surgical excision ranges from 0-20% in published literature.⁶⁰⁻⁶² One recent study,⁶² reported a 0% upstaging among women who would have fulfilled criteria for the LORIS trial, indicating that a low risk subgroup could be identified. The impact of a delay in diagnosis of invasive breast cancer or the development of invasive breast cancer while undergoing monitoring is thought to pose a low risk to patients if detected at an early stage, although this has not been definitively shown.

Additional risks to study participation include potential distress and loss of privacy when answering questions when filling out the surveys. While the direct responses to the survey will not be shared with the participants' medical team directly, we will alert the study team (registering physician and study coordinator at site) if a participant scores 10 or greater indicative of substantial depressive symptoms on the CES-D-10.

2 OBJECTIVES AND ENDPOINTS

This trial will compare both clinical outcomes and PRO between patients treated with surgery versus AM for biopsy-proven DCIS

Primary study outcomes. Endpoints were selected in two broad categories of 1) *Clinical Outcomes* defined as those disease- and treatment-related outcomes to be collected by research staff from primary source documentation, and 2) *Patient Reported Outcomes (PRO)* which will include comprehensive domains of QOL and psychosocial outcomes collected from patient surveys.

2.1 Primary Objectives

The hypothesis is based upon a non-inferiority endpoint that ***2-year rate of invasive breast cancer diagnosis is not inferior in the AM group compared to the surgery group.*** The estimate of invasive breast cancer upstaging (i.e. identified at the time of surgery) is 10% in the surgery group. Non-inferiority will be

declared if the 2-year detection of invasive breast cancer in the AM group does not exceed 15% (based on statistical estimates).

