10.2 Sample Size, Accrual Time and Study Duration

Power and Sample Size Considerations. Sample size for this study was estimated using a 2-group test of non-inferiority of proportions, with the 2-year invasive breast cancer rate in the surgery group assumed to be 0.10 based on published studies.^{61,62} The non-inferiority margin assumed was 0.05. Based on a 1-sided un-pooled z-test, with alpha=0.05, a sample size of n=446 per group will have 80% power⁶⁴ to detect the specified non-inferiority margin. The proportion of patients who decline the arm to which they are specifically randomized can diminish the estimate of treatment difference, and could also widen the confidence bounds, but the analytical approaches proposed here aim to diminish the impact on bias of the treatment difference. With a 3-year duration of accrual and 2 additional years of follow-up, we anticipate approximately 148 total events.

Analysis of Primary Outcome (See below for outcomes definitions). This trial was designed anticipating non-acceptance of arm allocation, and the proportion of patients that do not accept their arm allocation can lead to bias in estimates of treatment differences. Thus, we plan to complete several analyses of the primary outcome, reporting the primary intent to treat (ITT) analysis as well as sensitivity analyses that are intended to reduce the bias in estimation of treatment difference in this setting.

We assume that a clinically acceptable difference in 2-year invasive cancer diagnosis rate in order to conclude non-inferiority is 5%. Cumulative incidence curves will be used to estimate the invasive cancer diagnosis rates over time, and at the 2-year point, the difference in rates will be estimated and a 1-sided upper confidence bound of (AM-GCC) will be computed, using methods described by Austin.⁶⁵ We will conclude that AM is not inferior to Surgery if the upper confidence bound on the risk difference at 2 years is less than 5%.

ITT Analysis. The ITT analysis of 2-year invasive cancer diagnosis rate will be conducted using all patients, as randomized, and will be completed using Kaplan-Meier estimates, stratified by group, combined with the Greenwood's confidence interval. The difference in invasive cancer risks will be computed from the Cox model with treatment at 2 years, with a 1-sided 95% confidence interval of the difference (AM-GCC) computed.

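### Section 2.1 declares non-inferiority on the AM rate alone (at most 15%), while Section 10.2 requires the upper bound on the difference to be below 5 points; the two rules can give opposite conclusions

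*Combined protocol and SAP*

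**What the plan says.** Section 2.1 (Primary Objectives) opens with a comparative hypothesis, AM not inferior to surgery. It then gives a planning value: "The estimate of invasive breast cancer upstaging (i.e. identified at the time of surgery) is 10% in the surgery group". The decision rule follows: non-inferiority will be "declared if the 2-year detection of invasive breast cancer in the AM group does not exceed 15" percent, with a remark in brackets that this rests on statistical estimates. The sentence mentions neither the observed surgery rate nor a confidence bound.

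Section 10.2 gives a different rule. The trial will conclude that "AM is not inferior to Surgery if the upper confidence bound on the risk difference at 2 years is less than 5" percent, and the ITT paragraph fixes the level, "with a 1-sided 95% confidence interval of the difference (AM-GCC) computed". The sample size in the same section rests on this comparison: "with the 2-year invasive breast cancer rate in the surgery group assumed to be 0.10 based on published studies"; "The non-inferiority margin assumed was 0.05"; "Based on a 1-sided un-pooled z-test, with alpha=0.05, a sample size of n=446 per group will have 80% power".

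Both rules are in the current text. Nothing in the document says that 15% is illustrative or that Section 10.2 takes precedence.

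**The concern.** The 15% equals the assumed 10% surgery rate plus the 5-point margin. As a decision rule it agrees with Section 10.2 only if the surgery rate is exactly 10% and sampling error is ignored.

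The protocol does not treat 10% as assured. Section 1.6 says that "the estimate of upstaging to invasive cancer upon surgical excision ranges from 0-20% in published literature", and it cites one study with no upstaging among women who met another low-risk trial's criteria. If the surgery rate is well below 10%, AM could have two or three times as many invasive cancers and still come in under 15%. If the surgery rate is well above 10%, an AM arm that is truly equal to surgery could fail.

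A ceiling on one arm does not compare the randomised groups and does not control the type I error of the non-inferiority claim. With two written criteria for the primary conclusion, the result can be disputed, or the criterion chosen, once the data are known.

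**Working it through.** **Inputs.** From Section 10.2: surgery rate 0.10, margin 0.05, one-sided alpha 0.05, unpooled z-test, 80% power, 446 per group. From the synopsis and Section 4.2: 1,080 patients randomised 1:1, so 540 per arm. True rates other than 10% are illustrative assumptions. Complete 2-year follow-up is assumed, and simple proportions stand in for the planned Kaplan-Meier and Cox estimates.

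**The plan's own figure.** With equal true rates of 10%:

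n = (1.645 + 0.842)² × 2 × 0.10 × 0.90 / 0.05² = 445.1, so 446 per group.

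This reproduces the stated number. Power is 80.1% at 446 per arm and 86.3% at 540. The sample size was therefore built on the Section 10.2 rule.

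**The two rules on observed rates.** Let a and s be the observed AM and surgery rates.

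- Ceiling (Section 2.1, read as a point estimate): pass if a ≤ 0.15.
- Bound (Section 10.2): pass if U = (a − s) + 1.645 × √[a(1−a)/n + s(1−s)/n] < 0.05.

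Example at n = 446 with a = 0.14 and s = 0.10: the standard error is √(0.1204/446 + 0.0900/446) = 0.0217, so U = 0.04 + 1.645 × 0.0217 = 0.0757.

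| Observed AM | Observed surgery | U, n = 446 | U, n = 540 | Ceiling | Bound |
|---|---|---|---|---|---|
| 14% | 10% | 7.6 points | 7.2 points | pass | fail |
| 12% | 5% | 10.0 points | 9.8 points | pass | fail |
| 16% | 16% | 4.0 points | 3.7 points | fail | pass |

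Solving U = 0.05 at s = 0.10 gives the largest AM rate that passes the bound: about 11.6% at 446 per arm and 11.9% at 540. The ceiling allows 15%.

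**Probability of declaring non-inferiority.** For the ceiling this is the exact binomial P(X ≤ 0.15n) at the true AM rate. For the bound, the event U < 0.05 was summed over the exact binomial distributions of both arms. Figures are for 446 per arm, with 540 in brackets.

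| True AM | True surgery | Situation | Ceiling | Bound |
|---|---|---|---|---|
| 15% | 10% | at the margin | 48.5% (53.0%) | 5.2% (5.2%) |
| 10% | 5% | at the margin | 99.95% (99.99%) | 5.5% (5.3%) |
| 12% | 5% | beyond the margin | 96.8% (98.4%) | 0.4% (0.3%) |
| 10% | 10% | planning case | 99.95% (99.99%) | 80.2% (86.3%) |
| 15% | 15% | equal | 48.5% (53.0%) | 67.4% (74.5%) |
| 18% | 18% | equal | 4.2% (3.7%) | 61.9% (69.0%) |

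The normal approximation Φ((0.05 − d)/SE − 1.645), with d the true difference, gives bound figures within about 0.6 points of these. In the planning case the rules disagree in 19.8% (13.7%) of trials.

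**Alternative reading.** Suppose 15% is meant as a limit on the AM arm's own one-sided 95% upper bound. With AM at 12% and n = 446, that bound is 0.12 + 1.645 × √(0.12 × 0.88/446) = 14.5%, which passes. With surgery at 5%, the bound on the difference is 10.0 points, which fails. The conflict remains.

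**The case against.** The strongest reply is that 15% is shorthand. Section 2.1 begins with a two-arm hypothesis, gives 10% for surgery and then 15% for AM, and Section 10.2 supplies the 10% and the 5-point margin that add up to it. Section 10.2 is also complete: it gives direction, level, margin and decision. The synopsis, Section 2.3.1 and Section 10.1 all describe a comparison of arms, and no analysis section implements a one-arm test. A statistician working from Section 10 would apply the bound.

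Much of this stands. The 15% very probably did originate as 10% plus 5%. The pass rates above describe Section 2.1 taken literally as a point-estimate rule; they are not the error rate of the Section 10.2 analysis. The 0–20% range concerns upstaging at excision, whereas the endpoint is cumulative over 2 years, so the range shows that 10% is uncertain without fixing any alternative.

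The reply does not reconcile the two sentences. Section 2.1 uses the language of a decision. Reading it as shorthand still leaves 15% against about 11.6% when surgery is observed at exactly 10%, because the shorthand omits sampling error as well as the observed comparator.

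**Conclusion.** The concern holds, and the text must be corrected. The plan contains two criteria for its primary conclusion that conflict in both directions. At a true difference equal to the margin, the Section 2.1 rule passes about half of trials when surgery is at 10% and nearly all when it is at 5%, against about 5% for the Section 10.2 rule. With equal true rates of 15% or more, it fails an equal AM arm more often than the bound does.

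These sizes rest on complete follow-up, simple proportions and the illustrative true rates. Kaplan-Meier or Cox estimation would move the bounds slightly and would not bring the rules together. Only the Section 10.2 rule agrees with the 446 per group and keeps the one-sided type I error near its nominal 5%.

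**What to change.** Replace the decision sentence in Section 2.1 with the Section 10.2 rule, for example: *Non-inferiority will be declared if the one-sided 95% upper confidence bound on the difference (AM minus surgery) in the 2-year ipsilateral invasive breast cancer rate is below 5 percentage points.* If 10% and 15% are kept, label them as planning values and say that an AM rate at or below 15% is neither necessary nor sufficient.

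The suggested sentence also adds the word *ipsilateral*, which Section 2.1 lacks. It agrees with the synopsis and Section 2.3.1 and should be recorded as a deliberate second change.

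The cost is one sentence. Sample size, conduct and the Section 10.2 analysis stay as they are.

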2.2 Secondary Objectives

2.2.1 Quality of life and psychosocial outcomes:

The secondary hypothesis is based upon a non-inferiority endpoint that **2-, 5-, 6, 8, 10 health-related quality of life, rate of anxiety, and rate of depression are not inferior in the AM group compared to the surgery group.**

2.2.2 Clinical outcomes:

The secondary hypothesis is based upon a non-inferiority endpoint that **2-, 5-, 7- and 10-year rates of mastectomy, contralateral invasive breast cancer, and survival (both overall survival and invasive breast cancer-specific survival) are not inferior in the AM group compared to the surgery group.**

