Study Number	AFT-25
Study Type/Phase	Interventional Phase III Randomized Clinical Trial
Clinical Indication	Low-risk ductal carcinoma in situ (DCIS)
ClinicalTrials.gov Identifier	NCT02926911
IND Number	Not applicable
Number of Trial Patients	1,080
Estimated Duration of Trial	Accrual: 78 months (07/01/16- 12/31/22) Follow up: 2-, 5-, 7- and 10-years
Rationale	To study the risks and benefits of active monitoring (AM) compared to surgery in the setting of a pragmatic prospective randomized trial for low-risk DCIS. Our overarching hypothesis is that management of low-risk DCIS using an AM approach does not yield inferior invasive breast cancer or quality of life outcomes compared to surgery.

Primary Objective	To assess whether 2-year ipsilateral invasive breast cancer rate for AM is non-inferior to that for surgery.
Secondary Objectives	To determine whether AM is non-inferior to surgery for the following outcomes: 2-, 5-, 7- and 10-year mastectomy rate, breast conservation rate, contralateral invasive breast cancer rate, overall survival and invasive breast cancer specific survival; health-related QOL, anxiety and depression at baseline, 6 months, 1 year, annually year 2-6, biannually thereafter; coping at baseline; intolerance of uncertainty at baseline and 2 years.
Trial Design and Schema	Multicenter Phase III Prospective Randomized Trial comparing surgery to active monitoring with option of endocrine therapy (in both arms) for low-risk ductal carcinoma in situ (DCIS) (see Study Schema below)

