Emotional/Psychological: To assess generalized anxiety, we will use the **State Trait Anxiety Inventory (STAI)** scale.⁵¹ Depressive symptoms will be evaluated with the **Center for Epidemiologic Studies Depression Scale (CES-D-10)**.⁷⁷ The CES-D-10 will be scored automatically by PRO Core when it is completed online by the patient or when it is data entered by study staff at DFCI. If a participant scores

10 or greater, indicative of potential depression, the PRO Core system will automatically send an email to the site principal investigator, so that symptoms can be addressed as needed. In addition, site study personnel who log in to PRO Core will be able to see the flagged survey alert. Site study personnel must complete a brief form in Pro Core indicating that the flagged survey alert has been seen and triaged as appropriate. We will assess feelings of uncertainty using the **Intolerance of Uncertainty Scale** (Short-form), which has been used in studies of active monitoring in the prostate cancer setting.⁷²⁻⁷⁴ Coping will be evaluated using the **Brief COPE**, a shortened form of the COPE Inventory, inclusive of 28 items (14 subscales).⁷⁵

Decision-making: Four items (**The SURE scale**) adapted from the **Decisional Conflict Scale** will be used to measure patients' uncertainty about participating in the COMET trial.^{78, 79} The **Decision Regret Scale** will measure how women perceived their DCIS treatment/management decision including decision to participate in the trial.⁵² **Sources of information** about DCIS management options will be assessed using items adapted from a prior study of surgical decision-making.⁵³

Knowledge and Risk Perceptions: DCIS and breast cancer knowledge will be measured with items adapted from the **Breast Cancer Surgery Decision Quality Instrument (BCS-DQI)** as well as questions developed specifically for a study that assessed DCIS knowledge and risk perceptions.^{54,55,100} We will assess risk perceptions in women with DCIS using questions developed by Lerman and Croyle⁵⁶ that were used in a prior study of psychosocial outcomes in women with DCIS.¹⁸

Financial burden: We will adapt items from the **National Health Interview Survey**⁵⁷ and the **Cancer Outcomes Research and Surveillance (CanCORS) Caregiver Study**⁵⁸ to assess financial burden and to estimate out of pocket expenses attributed to their DCIS diagnosis.

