2.3 Endpoints

2.3.1 Primary endpoint:

Proportion of new diagnoses of ipsilateral invasive breast cancer in surgery and AM arms at follow up of 2-years.

2.3.2 Secondary endpoints:

- Quality of life and psychosocial outcomes;
 - Health related QOL at baseline, 6 months, 1 year, annually year 2-6, biannually thereafter.
 - Anxiety/depression at baseline, 6 months, 1 year, annually year 2-6, biannually thereafter.
 - Coping at baseline
 - Intolerance of uncertainty at baseline and 2 years
- Clinical outcomes
 - Mastectomy rate at 2, 5, 7 and 10 years
 - Breast conservation rate at 2, 5, 7 and 10 years
 - Contralateral invasive breast cancer rate at 2, 5, 7 and 10 years
 - Overall survival and invasive breast cancer-specific survival at 2, 5, 7, and 10 years
 - Ipsilateral invasive breast cancer rate in surgery and AM arms at 5, 7 and 10 years

2.3.3 Exploratory endpoints:

- Breast MRI utilization at 2, 5, 7 and 10 years
- Breast biopsy rate at 2, 5, 7 and 10 years
- Radiation rate at 2, 5, 7 and 10 years
- Chemotherapy rate at 2, 5, 7 and 10 years
- Self-reported co-morbidity at baseline, 6 months, 1 year, annually year 2-6, biannually thereafter.
- Adherence to hormonal therapy at 6 months, 1 year, annually year 2-6, biannually thereafter.
- Health behavior/lifestyle factors at 6 months and 2 years
- Symptoms, pain, body image, sexual function at baseline, 6 months, 1 year, annually year 2-6, biannually thereafter.

- Quality of decision making at baseline and 2 years
- Decisional regret at 1 year, annually year 2-6, biannually thereafter.
- Knowledge and risk perceptions at baseline and 2 years
- Decisional conflict at baseline
- Financial burden at 6 months
- Employment status at baseline, 6 months, 1 year, annually year 2-6, biannually thereafter.
- Use of complementary therapies at 6 and 24 months

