6.1.3 Patient Reported Outcomes

Survey instruments for the project have been carefully selected to provide the most relevant patient centered outcomes (see Section 1.3). Questionnaire packets will be completed at baseline, 6, 12, 24, 36, 48, 60, 72, 96, and 120 months; a gap year letter will be sent to participants at months 84 and 108 (the years when a survey packet is not being sent) from UNC PRO Core in the same way that they receive the survey packets (either by email or by mail). This patient-reported outcome data collection will be conducted using the PRO Core survey platform, which enables web-based questionnaire completion, automated email reminders, data entry of paper forms, and tracking of participant survey completion. Surveys will be available in English or in Spanish. Language preference for each participant will be noted in PRO Core at baseline and can be changed throughout the study. Detailed information (screenshots, etc.) about how to use PRO Core for this study is provided in the training slide deck. The baseline questionnaire will be completed on paper after the patient has registered for the study (but prior to randomization). It will be data-entered into PRO Core by the site study staff and a copy will be kept on file at the site. The baseline questionnaires should be uploaded to Pro-Core.

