Planned subgroup analyses (NCDB Special Study). The large DCIS registry developed through collaboration with the National Cancer Database (NCDB) will allow for the continued collection of long-term outcomes for patients as well as for the comparison of primary and secondary outcomes (when measurable in NCDB) for **AM versus surgery** amongst those patients who are randomized and accept their arm allocation versus those patients who are randomized but do not accept their arm allocation versus patients not registered or randomized to COMET, but who generally meet our broad inclusion criteria for the trial. Patients will be identified from all study sites during the time interval of COMET accrual. These analyses will be from predominantly non-randomized patients, so we plan to utilize observational study approaches for analyses. We will use full regression models (logistic or Cox model, dependent upon outcome measure) to control for potential confounders, including pathology, age, race, academic versus community setting, among others. As in other analyses, we will utilize inverse-probability weighting to handle missing data.⁷⁰

Analyses of long-term outcomes. Analyses of long-term outcomes will follow the approaches outlined above, modifying the year of rate calculations, accordingly. PRO data will utilize longitudinal linear mixed models over time, following appropriate scoring and transformation, if needed.

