10.5 Supplementary/Secondary Analysis Plans

Planned Analysis for PRO data: For analyses of PRO endpoints, we will use t-tests and ANOVA to compare unadjusted mean scores for health-related PRO measures at baseline. We will use linear mixed-effects models to assess change in these domains over time. Among women who are allocated to surgery, we will examine differences by surgery type (e.g., lumpectomy followed by radiation vs. unilateral mastectomy vs. bilateral mastectomy) and compare changes between these groups over time. In addition to baseline disease and socio-demographic data, information relating to other treatment (e.g., endocrine treatment, radiation) as well as co-morbidities will allow us to control for potential confounding by these factors. We will also analyze the decision-making, DCIS knowledge, and risk perception data at baseline and compare these domains between the surgery and AM groups. We plan to measure risk perceptions and knowledge again at 2 years and will assess change between the two time points in each group using t-tests (e.g., for continuous scores) and McNemar's test (e.g., proportion correctly perceiving their risk).

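### Secondary PRO objectives: non-inferiority is claimed on rates of anxiety and depression that the score-based analyses do not test, and, separately, on coping, which is measured only before randomisation

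*Combined protocol and SAP*

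**What the plan says.** **Hypotheses.** Section 2.2.1 states one non-inferiority hypothesis for years 2, 5, 6, 8 and 10. It covers health-related quality of life and continues "rate of anxiety, and rate of depression are not inferior in the AM group compared to the surgery group". The synopsis introduces its secondary objectives with "To determine whether AM is non-inferior to surgery for the following outcomes". That list names anxiety and depression without the word rate, and ends with "coping at baseline; intolerance of uncertainty at baseline and 2 years". Section 2.3.2 lists anxiety/depression and "Coping at baseline" among the secondary endpoints.

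**Analyses.** For PROs, section 10.5 says "we will use t-tests and ANOVA to compare unadjusted mean scores for health-related PRO measures at baseline", followed by linear mixed-effects models for change over time. The long-term paragraph of 10.2 adds "PRO data will utilize longitudinal linear mixed models over time, following appropriate scoring and transformation, if needed".

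**Case definitions.** Section 1.4 treats a CES-D-10 score of "10 or greater, indicative of potential depression" as the trigger for an alert to the site, and 1.6 repeats the threshold for that purpose. No cut-off is given for the STAI.

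**Timing.** Section 6.1.3 says "The baseline questionnaire will be completed on paper after the patient has registered for the study (but prior to randomization". Table 2 schedules the Brief COPE at baseline only.

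**The concern.** The hypothesis and the analysis are on different scales. A rate hypothesis asks how many women in each arm are anxious or depressed. A mixed model of scores asks whether the average differs. Two arms can share a mean and differ in the proportion above a threshold, so a finding of similar means could be reported as support for a statement about rates that nobody tested. The scale, the cut-off and the margin are all open in a trial without blinding (section 4.3), so they could be settled after the arm comparison has been seen. Psychological outcomes are part of the case for active monitoring (AM): the overarching hypothesis in 1.4 covers quality of life as well as invasive cancer.

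Coping has a different problem. An outcome recorded before randomisation cannot respond to the assigned arm, so a non-inferiority claim on it has no content whichever statistic is used.

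**Working it through.** **1. Hypothesis against analysis**

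| Element needed for a non-inferiority test | Anxiety | Depression | Health-related QOL |
|---|---|---|---|
| Scale in 2.2.1 | rate | rate | not stated; a score fits |
| Scale in 10.2 and 10.5 | score | score | score |
| Endpoint case definition | none | none (CES-D-10 of 10 or more is a site alert) | not needed for a score |
| Margin | none | none | none |
| Confidence-bound rule | none | none | none |
| Arm contrast at the named years | not stated | not stated | not stated |

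The 5% margin and upper-bound rule in 10.2 apply to the 2-year invasive cancer rate only. The long-term paragraph of 10.2 speaks of changing the year of the rate calculations, but its next sentence assigns PRO data to linear mixed models, so it does not supply a rate analysis. Section 10.5 does analyse one PRO proportion, by McNemar's test, but that is within-group change in risk perception.

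The data for either scale are already planned. Table 2 schedules the STAI-state and CES-D-10 at months 24, 60, 72, 96 and 120, which are years 2, 5, 6, 8 and 10.

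**2. Coping**

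The Brief COPE is given once, and the baseline survey precedes randomisation (sections 6 and 6.1.3). The null hypothesis of no arm effect is therefore true by design, and any difference is chance.

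**3. The plan's own figure, as a check on the method**

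Inputs from 10.2: control rate 0.10, margin 0.05, one-sided alpha 0.05, power 80%, unpooled variance.

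n = (1.645 + 0.842)² × 2 × 0.10 × 0.90 / 0.05² = 445.1, rounded up to 446 per group. This reproduces the stated figure. No corresponding figure exists for any PRO.

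**4. Why the scale and margin must be chosen (assumed inputs)**

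The documents give no anxiety or depression rate and no PRO margin, so the rates and margins below are assumptions. With 446 per group, a true difference of 0 and one-sided alpha 0.05, power = Φ(M / √(2p(1−p)/446) − 1.645).

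| Assumed rate p in both arms | Power, M = 0.05 | Power, M = 0.10 |
|---|---|---|
| 10% | 80% | over 99% |
| 15% | 67% | 99% |
| 20% | 59% | 98% |
| 25% | 53% | 96% |
| 30% | 49% | 95% |

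On the score scale, an assumed margin of 0.2 SD gives Φ(0.2 / √(2/446) − 1.645) = 91%.

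The scales do not convert at a fixed rate. For a normal score, a shift of 0.2 SD raises the proportion above a threshold by Φ(Φ⁻¹(p) + 0.2) − p. That is 4.0, 6.1 and 7.3 points at p = 10%, 20% and 30%.

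**5. Can equal means hide different rates? (assumed distributions)**

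Assume gamma-shaped CES-D-10 scores with the same mean in both arms, and take P(score ≥ 9.5) as the proportion scoring 10 or more.

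| Mean | SD in the two arms | Proportion scoring 10 or more | Difference (points) |
|---|---|---|---|
| 6 | 4 and 4 | 16.8% and 16.8% | 0.0 |
| 6 | 5 and 5.5 | 19.3% and 20.0% | 0.7 |
| 6 | 5 and 6 | 19.3% and 20.5% | 1.2 |
| 6 | 4 and 5 | 16.8% and 19.3% | 2.5 |
| 6 | 4 and 6 | 16.8% and 20.5% | 3.7 |
| 9 | 4 and 6 | 39.3% and 38.0% | −1.3 |

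A difference is possible, but its size and even its sign depend on inputs that the documents do not contain.

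**The case against.** The best defence is that rate is one loose word. For anxiety and depression it occurs in 2.2.1 alone; the synopsis and 2.3.2 omit it, and 2.3.2 does use it for mastectomy, breast conservation and contralateral cancer. On that view the endpoint list and the score analysis agree, and rewording 2.2.1 is enough. This stands in part: rewording is a legitimate route. It is not sufficient, because a score hypothesis of non-inferiority would still have no margin and no decision rule. Section 2.2.2 also uses rates in its ordinary sense for clinical events, so the plain reading of 2.2.1 is a proportion.

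It is also fair to say that the CES-D-10 threshold serves as a triage alert, so using it as an endpoint is a choice. Section 1.4 also refers to an appendix describing the scales, which is not in the text available for this review. Scoring detail could be there, but 10.2 and 10.5 would still specify no rate analysis.

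Some stronger readings are tempting and are not supported:

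- A reader might infer that no PRO proportion is analysed anywhere. Section 10.5 analyses one, for risk perception.
- A reader might infer that coping is part of the 2.2.1 hypothesis. It is not; the non-inferiority wording reaches coping only through the synopsis list, and its defect is timing, not the use of means.
- A reader might take 17% versus 21% as the expected effect on depression. Those figures need SDs of 4 and 6 at a common mean of 6, a 2.25-fold variance ratio with no basis in the documents.

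**Conclusion.** Both defects hold, and they are separate.

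1. Followed exactly, the plan does not test the rate hypotheses on anxiety and depression. It also has no rule by which non-inferiority on health-related quality of life could be concluded. This follows from comparing the text of 2.2.1, 10.2 and 10.5 and needs no numerical assumption.
2. Baseline coping cannot serve as a non-inferiority outcome or as a secondary endpoint of treatment.

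The reach is limited to secondary PRO objectives; the primary analysis is unaffected. No expected magnitude can be given. The power figures rest on assumed rates and margins. The equal-means illustration, about 0 to 4 points at mean 6 with the sign reversed at mean 9, shows only that means and rates are not interchangeable. The change should be made because it is cheap and because the choice loses value once outcomes have been compared by arm.

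**What to change.** **Anxiety, depression and quality of life.** Before outcome data are compared by arm, choose one scale and make 2.2.1, 2.3.2 and 10.5 agree.

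- *Scores:* reword 2.2.1 to CES-D-10 and STAI-state scores. Test the arm difference at each named year from the planned mixed model, adjusted for baseline. Report the proportion with CES-D-10 of 10 or more by arm, with a confidence interval, as a supporting analysis.
- *Rates:* define depression as CES-D-10 of 10 or more, the threshold already used to flag potential depression, and set a STAI-state cut-off in advance. Use a baseline-adjusted binary longitudinal model, for example GEE, giving a risk difference at each named year.

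On either route, state a non-inferiority margin and a one-sided confidence-bound rule for each PRO hypothesis, including health-related quality of life. A risk difference with an interval but no margin cannot conclude non-inferiority. If no margins can be justified, describe the PRO comparisons as estimation and drop the non-inferiority wording.

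**Coping.** Remove it from the synopsis non-inferiority list and from 2.3.2. Keep it as a baseline descriptor or, optionally, as an exploratory effect modifier; the latter would be a new analysis, since it is not among the subgroups in 10.2.

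**Cost.** Rewording of the objectives and analysis sections, agreement on margins, and at most one further model or summary per outcome. No added visit or instrument, and no change to treatment.
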